### **8.4 PACKAGING AND LABELING**

Each alirocumab treatment kit will be prepared to contain 6 pre-filled pens.

In addition to the alirocumab treatment kits, a training kit containing 1 placebo pre-filled pen will be prepared for the purpose of instructing patients or caregiver on injection administration.

The content of the labeling is in accordance with the local regulatory specifications and requirements.

### **8.5 STORAGE CONDITIONS AND SHELF LIFE**

Investigators or other authorized persons (eg, pharmacists) are responsible for storing the IMP in a secure and safe place in accordance with local regulations, labeling specifications, policies, and procedures.

Control of IMP storage conditions, especially control of temperature (eg, refrigerated storage) and information on in-use stability and instructions for handling the Sanofi compound should be managed according to the rules provided by the Sponsor.

The IMP will be stored in a refrigerator between +2°C and +8°C (36°F to 46° F) by the site. The temperature of the site refrigerator should be checked daily and recorded on a log sheet.

The IMP that will be stored at the investigational site should be kept in an appropriate locked room, under the responsibility of the Investigator or designee or other authorized person in accordance with the storage conditions indicated on the label.

After the supply of IMP kits to patients at the study site visits, appropriate provisions will be in place for transportation of the IMP kits from the study site to the patient's refrigerator.

### **8.6 RESPONSIBILITIES**

The Investigator, the hospital pharmacist, or other personnel allowed to store and dispense the IMP will be responsible for ensuring that the IMP used in the clinical trial is securely maintained as specified by the Sponsor and in accordance with applicable regulatory requirements.

All IMP will be dispensed in accordance with the Investigator's prescription and it is the Investigator's responsibility to ensure that an accurate record of IMP issued and returned is maintained.

Any quality issue noticed with the receipt or use of an IMP (deficiency in condition, appearance, pertaining documentation, labeling, expiration date, etc.) should be promptly notified to the Sponsor. Deficiencies related to the pre-filled pen should be recorded through a complaint procedure.

A potential defect in the quality of IMP may be subject to initiation of a recall procedure by the Sponsor. In this case, the Investigator will be responsible for promptly addressing any request made by the Sponsor, in order to recall IMP and eliminate potential hazards.

Under no circumstances will the Investigator supply IMP to a third party, allow the IMP to be used other than as directed by this clinical trial protocol, or dispose of IMP in any other manner.

#### **8.6.1 Treatment accountability and compliance**

- IMP accountability:
  - Used and unused treatment kits are returned by the patient at each visit,
  - The Investigator or designee counts the number of remaining unused pre-filled pens in the returned packs, fills in the Treatment Log Form,
  - The Investigator or designee records the dosing information on the appropriate page(s) of the CRF,
  - The monitor in charge of the study then checks the information by comparing the used or unused treatment kits with treatment log forms and source data.

IMP administration data will be recorded by the patients onto a patient's diary.

Measures taken to ensure and document IMP compliance and accountability are described below:

- The Investigator or designee will obtain via IVRS/IWRS the treatment kit number(s) and he/she will dispense the treatment kit(s) to the patient.

The accountability is to be performed at IMP kit re-supply visits only (see [Section 10.1.1](#)). The used and unused kit(s) should be brought back by the patient to such visits for accountability purposes.

- The Investigator or designee will complete the corresponding treatment log form.
- The monitor will check the data consistency between e-CRF pages, treatment log forms using patient's diary, IVRS transaction confirmations and returned unused pre-filled pen of a corresponding kit.

The patient will be instructed on the importance to stay under study treatment.

### **8.6.2 Return and/or destruction of treatments**

A detailed treatment log of the destroyed IMP will be established with the Investigator (or the pharmacist) and countersigned by the Investigator and the monitoring team. The Investigator will not destroy the unused IMP unless the Sponsor provides written authorization.

Sharp containers containing all used pens will be brought back on site by the patient for destruction purpose.

If the site is not able to destroy or destruction is not allowed in the country, all treatments kits will be retrieved by the Sponsor. A detailed treatment log of the returned IMP will be established with the Investigator or designee and countersigned by the Investigator and the Monitoring Team.

## **8.7 CONCOMITANT MEDICATION**

A concomitant medication is any treatment received by the patient concomitantly to the study.

Concomitant medications should be kept to a minimum during the study. However, if these are considered necessary for the patient's welfare and are unlikely to interfere with the IMP, they may be given at the discretion of the Investigator, with a stable dose (when possible). Besides the specific information related to concomitant medications provided in this Section, any other concomitant medication(s) will be allowed and will have to be recorded in the e-CRF and source data.

### **8.7.1 Management of background lipid-modifying therapy**

For background LMT, including statins, sites must follow the national product labeling for the safety monitoring and management of patients.

Throughout the whole treatment period, the patients should stay, as far as possible, on the stable maximally tolerated registered daily dose of statins, with or without other LMT that was received in the 4 weeks prior to screening visit.

Dose adjustment of LMT, including statins, might take place as per the investigator's judgment, for example in case of tolerability issue. Any adjustment will be documented in the e-CRF.

For adjustments based on LDL-C values, simultaneous adjustment in alirocumab dose and any LMT should be avoided, unless required for a safety/tolerability issue.

### **8.7.2 Contraception**

Women of childbearing potential must take an effective contraceptive method throughout the study treatment and during the 10-week period after the last study treatment injection. In some participating countries, specific contraceptive methods must be used by women of childbearing potential participating in a clinical trial (see Protocol [Appendix I](#) and [Appendix J](#)).

### **8.7.3 Prohibited concomitant medications**

Forbidden concomitant medications from the initial screening visit until the end of treatment visit include the following:

- Statins other than simvastatin, atorvastatin, rosuvastatin unless there is a documented intolerance to the above mentioned potent statins in which case other statins are allowed.
- Fibrates other than fenofibrate.
- Other PCSK9-inhibitor.
- Systemic corticosteroids, unless used as replacement therapy for pituitary/adrenal disease with a stable regimen for at least 6 weeks prior to randomization, are prohibited during the study duration.

### **8.7.4 Life style and dietary habits**

Life styles and dietary habits should be maintained if possible throughout the entire study duration, as medically feasible, with minimum changes.

## 9 ASSESSMENT OF INVESTIGATIONAL MEDICINAL PRODUCT

### 9.1 PRIMARY ENDPOINTS

In this study, primary endpoints only relate to safety assessments.

Safety will be assessed throughout the study by the following parameters:

- Recording of adverse events (including serious adverse events and adverse events of special interest).
- Standard laboratory tests: hematology (hemoglobin, WBC, platelet count) and biochemistry (urea, creatinine, glucose, glycated hemoglobin A1c [HbA1c], total CK).
- Liver function tests: SGOT (AST), SGPT (ALT), alkaline phosphatase (ALP), total bilirubin.
- Physical examination and vital signs: height (only at screening), weight, heart rate, systolic and diastolic blood pressure
- Device related complaints will be recorded and described as well.

Reporting procedures for AEs, SAEs and AESI are detailed in [Section 10.4](#), [Section 10.5](#), [Section 10.6](#), [Section 10.7](#).

The assessment of tolerability refers to local injection site reactions (see [Appendix H](#)).

#### 9.1.1 Adverse events

The observation of safety data will be as follows:

##### Pre-treatment period:

The Pre-treatment observation period is defined from the signed informed consent up to the first dose of IMP.

##### TEAE period:

The TEAE period will include a study period of 2 weeks after last study treatment injection. This means that TEAE period will cover a period from first dose to + 14 days after last dose. Safety reporting under commercial alirocumab intake will be documented via spontaneous reporting.

##### Death observation period:

The death observations are per the observation period defined above. In addition, “post- study” death includes all deaths reported after the end of the study (see definition of end of study period per patient in [Section 6.2.1](#)).

Adverse events, including AESIs and SAEs, will be collected from the time the patient signs the informed consent to the completion of the safety observation period.

All AEs will be coded to a “lowest level term (LLT)”, “preferred term (PT)”, “high level term (HLT)”, “high level group term (HLGT)” and associated primary “system organ class (SOC)” using the version of Medical Dictionary for Regulatory Activities (MedDRA) currently in effect at Sanofi at the time of the considered database lock.

Adverse events of special interest may be modified during a study by protocol amendment, which will enable the Company to collect additional information to better assess any potential and identified risks during the development.

For this study, the following AEs are AESI:

- Increase in alanine transaminase (ALT): ALT  $\geq 3 \times$  ULN (if baseline ALT  $<$  ULN) or ALT  $\geq 2$  times the baseline value (if baseline ALT  $\geq$  ULN).
- Allergic events and/or local injection site reaction that are allergic in nature and that require consultation with another physician for further evaluation.
- Pregnancy.
- Symptomatic overdose with IMP.
- Neurologic events that require additional examinations/procedures and/or referral to a specialist.
- Neurocognitive events.

Additional information can be found in [Section 10.4.1.3](#) and [Appendix E](#).

### **9.1.2 Safety laboratory**

The clinical laboratory data consist of urinalysis and blood analysis:

- Hematology (RBC count, hemoglobin, hematocrit, platelets, WBC count with differential blood count).
- Standard chemistry (fasting plasma glucose, sodium, potassium, chloride, bicarbonate, CPK, calcium, phosphorous, urea nitrogen, creatinine and calculated creatinine clearance using Cockcroft-Gault formula or eGFR using MDRD Study equation, uric acid, total protein, lactic dehydrogenase (LDH), albumin,  $\gamma$  Glutamyl Transferase [ $\gamma$ GT] Hepatitis B antigen, Hepatitis C antibody).
- HbA1c.
- Liver panel (ALT, AST, ALP, and total bilirubin).

Some additional safety laboratory parameters may be reflexively measured, based on actual data (please refer to [Section 10.4.5](#)).

Clinical laboratory values will be analyzed after conversion into standard international units. Standard international units will be used in all listings and tables.

### 9.1.3 Vital signs measurement

Vital signs include: heart rate, systolic and diastolic BP in sitting position.

## 9.2 SECONDARY ENDPOINTS

### 9.2.1 Secondary efficacy endpoints

The main efficacy secondary endpoint will be:

- The percent change in calculated LDL-C from baseline to Week 12 (main timepoint).

The key secondary efficacy endpoints will include:

- The proportion of patients reaching calculated LDL-C <100 mg/dL (2.59mmol/L) at Week 12.
- The proportion of patients reaching calculated LDL-C <70 mg/dL (1.81mmol/L) at Week 12.
- Proportion of patients with LDL-C <70 mg/dL (1.81 mmol/L) and/or  $\geq 50\%$  reduction from baseline in LDL-C (if LDL- C  $\geq 70$  mg/dL [1.81 mmol/L]) at Week 12.
- The percent change from baseline to Week 12 in non-HDL-C, total-C, HDL-C, and TG levels.

Since the study duration for each participating country will depend on when alirocumab becomes commercially available and reimbursed, with a minimum duration of patient's participation of 12 weeks and up to a maximum of 30 months, the secondary efficacy endpoints listed above will also be assessed at the following time points depending on countries: Weeks 4, 8, 12, 24, 48, 72, 96, 108, and EOT/EOS.

#### 9.2.1.1 Efficacy assessment method

##### 9.2.1.1.1 Lipid parameters

Total-C, HDL-C, TG, non-HDL-C will be directly measured by a local Laboratory as per the schedule in [Section 10.1](#).

LDL-C will be calculated using the Friedewald formula at all site visits.

Efficacy endpoints will not be considered as AEs, such as those involving abnormalities in lipid levels, unless meeting the criteria in [Section 10.4.2](#).

### 9.2.2 Other secondary endpoints

The other secondary efficacy endpoints will include:

- The proportion of patients who were up-titrated to 150 mg of alirocumab based on investigator's judgment.
- The proportion of patients who were down-titrated to 75 mg of alirocumab based on investigator's judgment.
- The reasons (ie, LDL-C threshold, AE) that triggered a down-titration or an up-titration of alirocumab.

### **9.2.3 Patient's reported outcomes: patient's acceptability of self-injection**

Patient's acceptability of self-injection will be documented by using the Self Injection Assessment Questionnaire (version 2 SIAQ, [Appendix G](#)), to be completed only by those patients who give themselves an injection.

This paper questionnaire will be collected separately from the e-CRF.

The SIAQ is a patient reported outcome (PRO) measure that contains two modules; one to be completed before the first self-injection (PRE module) and another to be completed after self-injection (POST module). The response for each item is provided on a five point Likert scale where a score of one corresponds to the patient's worst experience and a score of five corresponds to the best experience.

Some instructions to complete the questionnaire:

1/ the PRE Module must be completed before the training self-injection with placebo.

The PRE module consists of seven items that can be grouped into three domains: feelings about injections (items 1-3); self-confidence (items 4-6); and satisfaction with self-injection (item 7).

2/ the POST Module must be completed preferably within 30 minutes (maximum 1hour) after the self-injection of a SC medication.

The POST module consists of 18 items that can be grouped into six domains: feelings about injections (items 1-3); self-image (item 4); self-confidence (items 5-7); pain and skin reactions (items 8-9); ease of use (items 10-11); and satisfaction with self-injection (items 12-18). Domain scores are calculated as the mean of the item scores included in the domain.

The POST module will be completed at week 4, week 8, week 12, week 24, week 48, and then every 12 weeks until last alirocumab injection.

## **9.3 APPROPRIATENESS OF MEASUREMENTS**

See [Section 4](#).

## 10 STUDY PROCEDURES

For all visits after Day 1/Week 0 (inclusion visit), a timeframe of a certain number of days will be allowed. The window period for Week 0 up to Week 12 included is  $\pm 3$  days, then for Week 18 and Week 24 it is  $\pm 5$  days and then for the subsequent visits it is  $\pm 7$  days.

For all visits after Day 1/inclusion visit, if one visit date is changed, then the next visit should take place according to the original schedule as outlined in [Section 1.2](#).

### **Blood samplings:**

The blood samplings including the determination of lipid parameters (ie, total-C, LDL-C, HDL-C, TG, non-HDL-C, FPG and HbA1C) should be performed in the morning, in fasting condition (ie, overnight, at least 10 to 12 hours fast and refrain from smoking), and before IMP injection for all site visits throughout the study. Alcohol consumption within 48 hours and intense physical exercise within 24 hours preceding the blood sampling are discouraged.

*Note: if the patient is not in fasting conditions, the blood sample will not be collected and a new appointment will be given the day after (or as close as possible to this date) to the patient with instruction to be fasted (see above conditions) and not having taken IMP (injection to be delayed accordingly).*

In case the lipid results are made available during the visit, the lipid results performed at local laboratory will be reviewed at the on-site visit by the investigator, and, in case a dose adjustment is required, the dose will be modified immediately or the patient will be requested to come to the site within a few days for an unscheduled visit, so that the dose can be adjusted as needed.

The unscheduled dispensation visit will be similar to the “dispensation only” visits, eg, V10/W36.

### **Laboratory tests:**

The laboratory data are collected in accordance with the study schedule in [Section 1.2](#) and forwarded to the local Laboratory:

- Hematology: (all site visits except V2, V3/inclusion, V6/W8, dispensation visits and EOT/EOS: see [Section 9.2](#) for details).
- Chemistry: (all site visits except V2, V3/inclusion, V6/W8, dispensation visits, EOT/EOT): see [Section 9.2](#) for details.
- Lipid profile: (screening, Week 4, Week 8, Week 12, Week 24, Week 48, Week 72, Week 96, and EOT/EOS): see [Section 9.2.1.1.1](#).
- Liver panel: in case of total bilirubin values above the normal range, differentiation into conjugated and non-conjugated bilirubin will occur automatically (screening, Week 4, Week 8, Week 12, Week 24, Week 48, Week 72, Week 96, EOT/EOS): see [Section 9.2](#) for details.
- Hepatitis B surface antigen (screening).

- Hepatitis C antibody, at screening and EOT/EOS; in case of ALT increase during the study, hepatitis C antibody should be determined and if positive a reflexive testing should be performed).
- Serum pregnancy test (screening only).
- Urine pregnancy test (inclusion and EOT/EOS).

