h.	Safety evaluation: Adverse Events (AEs), product complaints, regardless of seriousness or relationship to alirocumab treatment, will be collected from the time the patient signs the informed consent form up to the EOT/EOS visit																	
i.	Review patient diary and treatment kit +data collection on study treatment administration.																	
j.	Repeat lab only in case of abnormality at EOT/EOS.																	
k.	New kit dispensation only if needed as per lab results.																	
l.	Hepatitis C only.																	
m.	Serum pregnancy test.																	
n.	Urine pregnancy test.																	

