### **Other assessments:**

All other blood parameters will also be measured by a local Laboratory during the study (as per the schedule in [Section 1.2](#), on blood samples taken preferably in the morning in fasting condition (at least 10 to 12 hours fast and refrain from smoking). Alcohol consumption within 48 hours and intense physical exercise within 24 hours preceding the blood sampling are discouraged.

- Glycemic parameters (HbA1c at screening, V7, V9, V11, V13, V15 and EOT/EOS visits and serum glucose at screening, V5, V7, V9, V11, V13, V15 and EOT/EOS visits) will be measured by a local Laboratory, as per the schedule in [Section 1.2](#).

Note: in case of high HbA1c values at screening, the Investigator is responsible for the optimization of the patient's treatment to achieve HbA1c targets as defined by local guidelines or the Standards of Medical Care in Diabetes-2012 by the American Diabetes Association.

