**During the EOT/EOS visit the below will be performed:**

- Collect AEs.
- Check product complaints.
- Check compliance on IMP (review patient diary and treatment kit) and data collection on IMP administration.
- Record concomitant medication.
- Perform physical examination.
- Take vital signs including HR and BP.
- Laboratory tests: Hematology, Biochemistry, Liver panel (including Hepatitis C antibody, with reflexive testing if positive), Lipid profile, HbA1c. In case of abnormal results, a retest should be performed as soon as possible.
- Urinalysis (dipstick and if abnormal then microscopy).
- Urine pregnancy test (women of childbearing potential only).
- Document the end of treatment with collection of the following:
  - Last dose as per diary,
  - Reason for permanent treatment discontinuation,
  - Whether the patient switches to commercial alirocumab or to another therapy.
- Remind Nutritional Counseling (including reviewing patient's diet).
- IVRS/IWRS contact to register the patient's EOT/EOS.

Reminders:

- An appointment for lab sampling will be scheduled in case of any persistent laboratory abnormality at EOT/EOS visit.

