#### **2.1.4.3 *Laboratory safety variables***

The clinical laboratory data consist of urinalysis and blood analysis.

Blood samples for laboratory tests are drawn at screening visit, Week 4 (except HbA1c), Week 8 (only for liver panel), Week 12, Week 24, Week 48, Week 72, Week 96 and EOT/EOS. Hepatitis B antigen is measured at screening only and Hepatitis C antibody at screening and at EOT/EOS. Serum pregnancy test is performed at screening and urine pregnancy test is performed at inclusion and at the end of study.

- Hematology (red blood cells [RBC] count, hemoglobin, hematocrit, platelets, white blood cells [WBC] count with differential blood count).
- Standard chemistry (fasting plasma glucose, sodium, potassium, chloride, bicarbonate, CPK, calcium, phosphorous, urea nitrogen, creatinine and calculated creatinine clearance using Cockcroft-Gault formula or Estimated Glomerular Filtration Rate [eGFR] using modification of the diet in renal disease (MDRD) Study equation, uric acid, total protein, lactic dehydrogenase (LDH), albumin,  $\gamma$ -Glutamyl Transferase [ $\gamma$ GT] Hepatitis B antigen, Hepatitis C antibody).
- HbA1c.
- Liver panel (ALT, aspartate aminotransferase [AST], alkaline phosphatase [ALP], and total bilirubin).
- Serum and urine pregnancy test.

Urinalysis - dipstick is performed at site or at the local Laboratory at screening, inclusion, Week 12, EOT/EOS visits and as needed during the study at investigator's discretion. It will assess for WBC, RBC, pH, specific gravity (qualitative/quantitative), and for the presence of blood, protein, glucose, ketones, nitrates, leukocyte esterase, uro-bilinogen and bilirubin.

Technical formulas are described in [Section 2.5.1](#).

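### Protocol section 10 lists the final visit among those without chemistry, and most naturally without hematology, although the EOT/EOS checklist and the SAP require both panels there

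*Protocol*

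**What the plan says.** The 'Laboratory tests' paragraph of Protocol section 10 opens by deferring to the flow chart in section 1.2: "The laboratory data are collected in accordance with the study schedule in" that section. Its bullets then restate the schedule test by test.

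- Hematology: "all site visits except V2, V3/inclusion, V6/W8, dispensation visits and EOT/EOS".
- Chemistry: "all site visits except V2, V3/inclusion, V6/W8, dispensation visits, EOT/EOT".
- Lipid profile and liver panel: the visits are listed one by one, and EOT/EOS is among them.

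Other parts of the documents bear on the same visit.

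- The EOT/EOS checklist in Protocol 10.1.2.5 begins its blood work with "Laboratory tests: Hematology, Biochemistry, Liver panel" and adds a prompt retest if results are abnormal.
- 'Other assessments' in section 10 schedules "serum glucose at screening, V5, V7, V9, V11, V13, V15 and EOT/EOS visits". Protocol 9.1.2 places glucose in the chemistry panel: "Standard chemistry (fasting plasma glucose, sodium, potassium, chloride, bicarbonate, CPK, calcium, phosphorous, urea nitrogen, creatinine".
- Flow chart footnote j reads "Repeat lab only in case of abnormality at EOT/EOS".
- SAP 2.1.4.3 gives blood sampling at screening, Week 4, Week 8, "Week 12, Week 24, Week 48, Week 72, Week 96 and EOT/EOS". Its only exceptions are HbA1c at Week 4 and Week 8, where only the liver panel is drawn.

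**The concern.** Taken at their word, the two bullets drop hematology and chemistry from the last visit, while the rest of the Protocol and the SAP expect them. Safety is the primary endpoint. Protocol 9.1 names hemoglobin, white cells, platelets, urea, creatinine, glucose and total CK among its laboratory components, and EOT/EOS is their last scheduled check. At stake are the final blood counts, creatinine and eGFR, CPK and electrolytes of any patient whose site works from the bullets. Liver panel, lipids, HbA1c, glucose, hepatitis C antibody and urinalysis at EOT/EOS are scheduled in their own right and are not affected.

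**Working it through.** There is no figure in the plan to reproduce. The check has two parts: a comparison of the schedules, and the age of the last scheduled value if the EOT/EOS sample is missed.

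**1. Are the panels scheduled at EOT/EOS?**

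| Source | Hematology | Chemistry |
|---|---|---|
| Protocol 10, 'Laboratory tests' bullets | No, on the natural reading ('and' is ambiguous) | No (typed 'EOT/EOT') |
| Protocol 10.1.2.5 checklist | Yes | Yes |
| Protocol 10, 'Other assessments' | Silent | Yes, for glucose |
| SAP 2.1.4.3 | Yes | Yes |
| Flow chart footnote j | Indirect yes | Indirect yes |

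The checklist and the SAP settle the matter for both panels without further help. The glucose schedule adds support for chemistry only. Footnote j is weaker: a repeat after an abnormal EOT/EOS result implies a first sample, but the note is loosely worded. The flow chart's tick positions are not used, because its columns are shifted in the text available for review.

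**2. Age of the last scheduled value if the EOT/EOS sample is missed**

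Inputs: Protocol 10.1.2.3 schedules both panels at Week 4 (Day 29), Week 12 (Day 85), Week 24 (Day 169), Week 48 (Day 337), Week 72 (Day 505) and Week 96 (Day 673). It does not require them at Week 8. Protocol 10.1.2.5 puts EOT/EOS at Day 841, or earlier if the commercial product becomes available. Nominal days are used and visit windows are ignored.

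Formula: largest gap = day of the next scheduled panel (or Day 841) − day of the previous one.

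- EOT/EOS between Weeks 12 and 24: 169 − 85 = 84 days = 12 weeks. The bound is approached but not reached, because at Week 24 itself both panels are due under 10.1.2.3.
- EOT/EOS after Week 24: 337 − 169 = 505 − 337 = 673 − 505 = 168 days = 24 weeks, again approached from below.
- EOT/EOS at Week 120: 841 − 673 = 168 days = 24 weeks, reached exactly, because Week 120 has no other scheduled panel.
- Short end: if the last scheduled sample was drawn on the day of the last injection and EOT/EOS follows 14 days later, the gap is 14 days.

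**The case against.** The strongest reply is that the correct instruction already governs. The paragraph defers to the flow chart, the checklist that staff use on the day names both panels, and the SAP agrees. A sample is lost only if a site relies on the bullets and on neither of the other two. This stands, and it is why the point is minor. It does not make the bullets correct. Their other cross-reference does not help either: it sends the reader to section 9.2 on secondary endpoints, while the safety laboratory content is in 9.1.2.

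The wording can also be defended. The hematology bullet can be read as all site visits with certain exceptions, plus EOT/EOS. That reading is available, so a reader should not infer that both bullets exclude the visit beyond doubt. It fails for chemistry, where there is no 'and' and the mistyped entry is simply the last item in the list of exceptions.

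Footnote j could be taken to mean that laboratory work is repeated at EOT/EOS only after an earlier abnormality, which would fit the exclusion. The lipid and liver rows carry the same mark, and the bullets schedule those two at EOT/EOS without condition, so that reading is unlikely. The note is still only indirect support.

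Three stronger inferences are tempting but not supported.

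- That the error carries over to the early-discontinuation visit. Protocol 10.3.2.2 calls for the end-of-treatment assessments, and the list of these in 10.1.2.5 is correct.
- That an EOT/EOS falling at Week 12 would leave values 85 − 29 = 56 days old. Week 12 is Visit 7, which requires both panels under 10.1.2.3, and the bullets do not exempt it.
- That a results table would change. SAP Table 3 has no EOT/EOS row. The SAP's treatment-emergent period ends 14 days after the last injection, whereas the visit falls 14 to 21 days after it, so many of these samples would lie outside the abnormality counts in any case.

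**Conclusion.** The inconsistency is real and the bullets are the outlier. For chemistry the text plainly excludes a visit at which the EOT/EOS checklist, the glucose schedule and the SAP require the test. For hematology it most naturally does so, against the checklist and the SAP.

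The consequence is conditional and probably uncommon: a missed final safety sample at a site that follows the bullets alone. The last scheduled values would then be between about 14 days and nearly 12 weeks old for an EOT/EOS between Weeks 12 and 24, and up to 24 weeks old for a later one. These figures assume nominal visit days, attendance at all earlier visits and no unscheduled blood test in between. They do not cover patients who stop before Week 12. The documents give no basis for estimating how many sites would be misled, and no bias or change in a reported result is claimed. Severity: minor.

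**What to change.** In the 'Laboratory tests' paragraph of Protocol section 10, delete 'EOT/EOS' from the exceptions in the hematology bullet and 'EOT/EOT' from those in the chemistry bullet. State in each that the panel is done at EOT/EOS, so that the bullets match Protocol 10.1.2.5 and SAP 2.1.4.3. Notify sites of the correction.

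The cost is a change to two bullets, by amendment or site clarification letter. It adds no visit and no blood sample, and the SAP needs no change.
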